6.1. Selection of First-Line Treatment

6.1.1. First-Line Treatment in Patients With Favorable- to Intermediate-Risk Clear Cell mRCC

Currently, Phase III data originating from four randomized trials support the use of three molecules in the first-line setting, ie, Sunitinib,^{5,6} pazopanib,⁷ and bevacizumab, in combination with interferon- α .^{8,9} The criteria for choosing between Sunitinib and pazopanib currently represent the hottest topic of debate. Its importance prompted the design and conduct of the first head-to-head Phase III trial comparing two first-line treatment alternatives for mRCC patients.¹⁰

A head-to-head prospective Phase III trial of Sunitinib and pazopanib [COMPARZ], ClinicalTrials.gov identifier NCT00720941¹⁰ the randomized design rested on the non-inferiority comparative effectiveness of 800 mg once daily continuous dosing of pazopanib relative to 50 mg once daily 4/2 weeks dosing of sunitinib. Although there is no doubt that direct comparison of Sunitinib versus pazopanib represents an effort aimed at providing evidence data in regards to two management alternatives for clear cell mRCC patients, many questions pertaining to study results and their interpretation remain unanswered.

The observation of differences in patterns of care between community and academic practice dovetails with other retrospective reports. Choueiri et al. published a series of 144 RCC patients from two tertiary oncology centers in the US. Patients were treated with Sunitinib, sorafenib, or bevacizumab from 2003 to 2008. Treatment patterns, response rates, and adverse events were described.¹² Similar data were obtained from a retrospective review of 250 patients with mRCC treated at 18 community oncology clinics. Differences in outcomes between these two studies included median duration of first line therapy for both Sunitinib (5.9 months in the community vs. 10.5 months in the academic centers) and sorafenib (5.5 vs. 8.1 months). In addition, patients in the community were more likely to receive lower doses of Sunitinib and sorafenib and were more likely to have dose reductions and interruptions than patient in the academic centers. These differences in practice patterns are an important area of further research and may lead to the understanding of more optimal treatment regimens for patients.¹³

A study was conducted based on medical records of 291 patients in 5 countries showed that using first line Sunitinib on naïve treatment patients exposed those patients to adverse events. Those adverse events consequently affected the alteration of treatment in the first months. Thus, outcome was not optimal. On the other hand, using Sunitinib as first line showed longer time to progression, more tumor size decrease, longer OS, higher response probability.¹⁴ Although first line Sunitinib was associated with adverse events, they were mild to moderate.¹⁵

It has been shown that dose reduction or interruption is required for 50% of the patients in order to control the adverse events.¹⁶ Toxicity management through using dynamic approaches such as alternative schedules positively impact the treatment outcome.¹⁷

The Rainbow study proved that provision of alternative schedule 2/1 in selected patients enhances the safety profile and reduces toxicities such as hypertension and fatigue.¹⁸

Other troublesome toxicities such as hand-foot syndrome, mucositis and thrombocytopenia were significantly decreased for mRCC patients who switched from 4/2 to 2/1 schedule.¹⁹

Consequently, the alleviation of Sunitinib toxicities exposed mRCC patients to significant improvement of the HRQOL.²⁰

6.2. Selection of Second-Line Treatment

Treatment sequencing in second-line after first-line TKI failure may consist of either a second-line TKI or a second-line mammalian target of rapamycin (mTOR) inhibitor or recently immunotherapy integration.²¹⁻²⁴

Given the availability of multiple new mRCC targeted agents that have been approved within the last 7 years and new agents expected to launch in the next several years, it is important to understand real world mRCC practice patterns in the Middle East & Africa. Clinical trial populations will not suffice as they are not representative of real-life populations of patients given the selection criteria and specific focus on a single drug or line of therapy. As of January 2016, there are no prospective longitudinal mRCC registries in that region that could be identified in www.clinicaltrials.gov website or in the published literature/abstracts other than the studies described above. Clearly, a prospective study reflecting longitudinal treatment patterns and outcomes in academic and community practice is needed.

The overall aim of the study is to describe patterns of treatment and outcomes across multiple lines of treatment in the mRCC setting, among newly diagnosed patients treated in Middle East & North Africa.

7. RESEARCH QUESTION AND OBJECTIVES

7.1. Objective

The primary goal of this prospective, observational Phase IV study is to provide knowledge regarding the use of SU as first line treatment as well as 2nd line SU- different sequence with respect to efficacy outcomes, adverse events and health related quality of life (QoL) in the real life setting.

Primary Objective:

To assess the impact of SU as 1st line treatment on Progression Free Survival (PFS) and on Time to Treatment Failure (TTF) for patients with adv/ mRCC.

Secondary Objective:

- To assess the Objective Response Rate (ORR) for adv/ mRCC patients receiving SU as 1st line treatment.
- To describe the usage of different doses of SU in these patients in terms of: dosing change, dosing schedules and the average dose received during the SU period treatment.

- To assess the impact of the 2nd line sequence SU- different treatment on combined PFS and TTF for patients with adv/mRCC and according to the second line post SU treatment (TK1,mTOR).
- To describe the safety of 2nd line SU-different sequence treatment and the tolerability of patients receiving it.
- To measure Quality of Life (QoL).

The study will collect data based on selection criteria for SU, including therapy management, treatment tolerance and safety among others.

Moreover, this study will collect and assess information on the sequence therapies (SU- different) used such as duration, the drivers of physician selection of particular agents as first & second lines, changes in therapy over time, dose modifications, discontinuation/interruptions of therapies, disease staging, toxicity from treatment and survival post stopping therapy.

Subsequent therapy post SU will also be documented. The following treatment outcomes will also be assessed:

- Treatment patterns (dose/duration) for SU.
- Patterns of toxicity exhibited by patients.

CCI

8. RESEARCH METHODS

8.1. Study Design

OPTIMISE is an international (AfME), prospective, non-interventional, non-controlled, observational multicenter study.

Patients will be enrolled from several AfME countries including Algeria, Morocco, Tunisia, Egypt, UAE, Qatar & South Africa. Investigators will be specialists, in charge of adv/mRCC. These sites involved (at least when performing feasibility) will be representative of their respective country in terms of practice. Participating physicians will not be influenced in their decision making and routine proceedings in any way.

[figure not shown]
Primary outcome measure will assess PFS in patients receiving the SU and in patients receiving a second line treatment post SU; as well as TTF for patients with adv /mRCC.

Patients will be enrolled when they start a treatment with SU on 1st line. Patients enrolled at SU initiation, will be followed-up whatever the post SU-2nd line treatment is (AXI, other drugs, no further active treatment, (supportive care)). The possible 1st and 2nd line sequences of treatment under investigation (ie, patient pools) will be ([Figure 1](#)):

- SU-AXI.
- SU- other second line treatment (sorafenib, pazopanib, everolimus, temsirolimus, other).
- SU- not further active treatment (supportive care). The study will include a prospective data collection:
 - Prospective data will also be collected for all patients enrolled in the study at SU- 1st line level, irrespective of 2nd line treatment, or no further active treatment;
 - Prospective data in terms of medical treatment records, will be collected for all 2nd line patients.

The inclusion period of eligible patients is planned for 12 months, with minimum of 1 year follow-up period. Patients will be followed-up from their enrollment to the end of the study follow-up period.

Figure 1. Study Flow Chart

8.2. Setting

The study will enroll patients according to the eligibility criteria in participating countries across Africa Middle East. The recruiting centers will be representative of each country involved in terms of care management systems, of size and of practices (at least when performing feasibility).

Any patient who meets the eligibility criteria will be invited to participate in the study with no biased selection by the investigators. The enrollment visit will be performed at the time of the patients' inclusion, after the patients' acceptance of enrollment in the study.

Data will come from medical records and will be collected in routine clinical practice. The enrollment visit will comprise a first section on patients' eligibility for every patient whatever pool they belong to and a second section on SU treatment started at the inclusion.

Follow-up will be ensured during visits in the context of usual patients' care management (non-interventional study). No extra visits will be required by the protocol of the study.

As long as the patients are treated with SU as first line, every visit to the center will be recorded. In accordance with ESMO guidelines and physicians clinical practice is real life, follow-up visits are approximately expected:

- During SU treatment: every 6 weeks (every cycle) with tumor assessment approximately every 3 months with respect to the clinical practice.
- When patients come off SU treatment (and after receiving the SU-2nd line sequence) they will be followed-up every 6 months (separate form) for survival until the end of the study.
- A deviation of +/- 6 weeks (1.5 months) is acceptable window for the follow-up visits.

As the inclusion criteria (patients being treated with SU in 1st line according to the approved therapeutic indication), the medication prescribed within the regular practice of the physician. In addition, as of the non-interventional nature of the study, there will be no specific requirements with regards to the treatment process. The physician will determine dosage and duration of the treatment, guided by the local country approved Prescribing Information and according to his assessment of the individual therapeutic needs of the patient.

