3.5. Setting

The study will enroll patients according to the eligibility criteria in participating countries across Africa Middle East. The recruiting centers will be representative of each country involved in terms of care management systems, of size and of practices (at least when performing feasibility).

Any patient who meets the eligibility criteria will be invited to participate in the study with no selection by the investigators. The enrollment visit will be performed at the time of the patients' inclusion, after the patients' acceptance of enrollment in the study.

Data will come from medical records and will be collected in routine clinical practice. The enrollment visit will comprise a first section on patients' eligibility for every patient.

Follow-up will be ensured during visits in the context of usual patients' care management (non-interventional study). As long as the patients are treated with SU, AXI, other TKI (sorafenib, pazopanib everolimus, temsirolimus, other) or no further active treatment (supportive care), every visit to the center will be recorded. In accordance with ESMO guidelines and physicians clinical practice is real life, follow-up visits are approximately expected as below:

- During SU treatment: every 6 weeks (every cycle) with tumor assessment approximately every 3 months with respect to the clinical practice.
- When patients come off SU treatment: they will be followed-up every 6 months for survival until the end of the study.
- A deviation of +/- 6 weeks (1.5 months) is acceptable window for the follow-up visits.

Because of the inclusion criteria (patients being treated with SU in 1st line according to the approved therapeutic indication), the medication prescribed within the regular practice of the physician. Because of the non-interventional nature of the study, there will be no specific requirements in regards to the treatment process. The physician will determine dosage and duration of the treatment as guided by the local approved country. Prescribing information will be according to his assessment of the individual therapeutic needs of the patient.

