8.5.3. Follow-up Phase

For each subject, after treatment, there would be two follow-up visits (Visit 6-7) in one year, one visit every 6 months (month 18 and 24).

- Concomitant medications (a window period of 28 days prior to the start of the study treatment, during the study and up to 28 days post the last dose of treatment applies).
- Adverse Events Assessment.
- Update in Disease Status (including PFS, RR, TTR, TTF, OS).
- Update in Treatment Status/ Change in therapy.
- Reporting of routine labs collected.

- Performance Status (ECOG), weight (BMI) and blood pressure.
- QOL questionnaire (FKSI 19) ([Appendix 1](#)).

In case of no treatment failure till month 12, more treatment visits will be scheduled until SU discontinuation.

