4.2. Subgroups

4.2.1. Subgroups to meet primary and secondary objectives

- Compare efficacy parameters (PFS, OS) for the combined 1st line SU- 2nd line sequences according to the second line post SU :
 - SU in 1st line-Axitinib TKI in 2nd line
 - SU in 1st line- other TKI in 2nd line (sorafenib, pazopanib)
 - SU in 1st line/mTOR in 2nd line (temsirolimus, everolimus)

CCI [REDACTED]

- [REDACTED]
- [REDACTED]
- [REDACTED]
- [REDACTED]
- [REDACTED]

[figure not shown] 2);

- Incidence of other AEs (grade ≤ 2);
- Incidence of all AE per grade.
- AEs will be analyzed separately for AEs related to SU as solicited and unsolicited AE.
- **Discontinuation due to toxicity**
 - Proportion of patients who discontinued the treatment of interest, because of AEs;
 - Treatment duration until discontinuation for AEs;
- **Deaths**
 - Proportion of patients who died due to any cause, over the treatment period (including the 28 days after the treatment discontinuation) and along the study;
 - Cause of death (tumor-related, other cause).

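### Protocol 8.2, 3.5, 8.4.1 and 8.5.3 give different rules for what is recorded once a patient stops first-line sunitinib, so post-sunitinib progression and second-line data may be captured unevenly, sparsely or late

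*Protocol*

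**What the plan says.** **Which visits are recorded.** Protocol 8.2 says: "As long as the patients are treated with SU as first line, every visit to the center will be recorded". The matching sentence in Protocol 3.5 opens: "As long as the patients are treated with SU, AXI, other TKI (sorafenib, pazopanib everolimus, temsirolimus, other) or no further active treatment (supportive care", so it also covers second-line treatment and supportive care.

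**What follows SU.** Protocol 8.2: "When patients come off SU treatment (and after receiving the SU-2nd line sequence) they will be followed-up every 6 months (separate form) for survival". Protocol 3.5: "When patients come off SU treatment: they will be followed-up every 6 months for survival until the end of the study". The interval and purpose are the same, but the reference to second line is absent from 3.5. Both sections place tumor assessment, roughly every three months, under the bullet for SU treatment and give no timing after it. The visit window is wide: "A deviation of +/- 6 weeks (1.5 months) is acceptable window for the follow-up visits".

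**What the schedule asks for.** The table in Protocol 8.4.1 marks adverse events, disease status and treatment status at months 3, 6, 9 and 12 (headed as the treatment phase), at months 18 and 24 (follow-up phase) and at end of study. Protocol 8.5.3 says: "For each subject, after treatment, there would be two follow-up visits (Visit 6-7) in one year, one visit every 6 months (month 18 and 24". It lists the same items for those visits, together with labs, performance status and QoL.

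**What the endpoints need.** PFS (Protocol 3.3.3 and SAP Appendix 3) runs from the first SU dose to progression or death and does not stop when SU stops. Combined PFS and combined TTF end during or at the end of second line. SAP 8.2 plans a safety and tolerability analysis of the SU–other sequence. Protocol 3.4 and 8.1 also name PFS in second-line patients within the primary outcome measure.

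**The concern.** A coordinator whose patient has just stopped SU cannot tell from the protocol what to enter next. Depending on the section read, the answer is every routine visit, a six-monthly survival form, or a scheduled update of adverse events, disease and treatment. Several endpoints depend on exactly this period. A patient who stops SU for toxicity without progression still has an open PFS clock, and the date of a later progression must come from somewhere. Combined PFS, combined TTF and safety of the sequence depend entirely on what is recorded during second line.

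With 14 sites in seven countries, different readings would give data of different density at different sites. Where contacts are sparse, progression tends to be dated late. Pooling cannot repair that afterwards.

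**Working it through.** The plan gives no figure for this point, so the check is a comparison of the texts, then an estimate of how many patients are affected and how late the dating could be.

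**1. One patient, five rules.** Take a patient who stops SU in month 2 for toxicity, without progression, and later starts second line.

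| Source | What happens next |
|---|---|
| 3.5, recording sentence | Every visit recorded during second line or supportive care |
| 3.5, post-SU bullet | Survival contact about 6 months after stopping, near month 8 |
| 8.2, bullet read as starting at SU stop | As above, on a separate form |
| 8.2, bullet read as starting after second line | Survival contact only after second line; 8.2 has no recording rule or assessment timing for second line itself |
| 8.4.1 and 8.5.3 | Adverse events, disease and treatment status at months 3, 6, 9 and 12 if the treatment-phase columns still apply off SU, which is not stated; then at months 18 and 24 |

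The first two rows are both in 3.5, so that section conflicts with itself. Protocol 8.5.3 has the same six-month spacing as 8.2 and 3.5. It differs from them in content, not interval.

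**2. How many patients are off SU.** Inputs: 140 patients (Protocol 8.7), and median first-line SU durations of 5.9 months (community) and 10.5 months (academic) from the chart reviews in Protocol 6.1.1. Exponential stopping is my assumption. Fraction off SU by month t = 1 − 0.5^(t/median).

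- Month 3, median 5.9: 1 − 0.5^(3/5.9) = 29.7%; × 140 = 41.6
- Month 3, median 10.5: 1 − 0.5^(3/10.5) = 18.0%; × 140 = 25.2
- Month 12, median 5.9: 1 − 0.5^(12/5.9) = 75.6%; × 140 = 105.8
- Month 12, median 10.5: 1 − 0.5^(12/10.5) = 54.7%; × 140 = 76.6

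This gives about 25 to 42 patients by month 3 and 77 to 106 by month 12. The counts cover stopping for any reason. Patients who stopped at progression or death already have their first-line PFS event, so only the remainder can bias first-line PFS. The documents give no split.

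**3. Spacing of contacts.** With ±1.5 months at each end, consecutive six-monthly contacts can be 6 ± 3 = 3 to 9 months apart, and three-monthly visits 3 ± 3 = 0 to 6 months apart.

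**4. Illustration of late dating.** Suppose progression is seen only at study contacts and falls at random between them. The mean delay is then half the interval: 3/2 = 1.5 months against 6/2 = 3.0 months. A simulation with exponential progression times and true medians of 4, 6, 8 and 11 months agreed. The recorded median was 1.5 to 1.6 months late with three-monthly visits and 3.1 to 3.3 months late with six-monthly ones. For a true median of 6 months, the recorded values were 7.5 and 9.2. These shifts apply if every patient is observed that way. For first-line PFS the effect would be diluted, because only patients who stop SU before progression are exposed to it.

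**The case against.** The strongest reply is that the plan does provide for post-SU data. Protocol 7.1 lists subsequent therapy, toxicity and survival after stopping. Protocol 8.1 promises prospective data on all enrolled patients whatever the second line, and treatment records for second-line patients. Protocol 8.5.3 collects adverse events and disease status after treatment. Protocol 10.1.1 follows SU-related events to resolution, and 10.1.2 keeps safety reporting open to the end of observation. Data come from routine charts, so a scan date may be available even when no study contact falls near it. The study specifies no visits (8.5) and is hypothesis-generating (8.11).

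Most of this stands, and it rules out some stronger readings:

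- A reader might infer that 8.2 records visits only during SU and that later events are missed. 8.2 does not say only, its survival bullet carries the second-line qualifier, and the sections above require later data.
- A reader might take 3.5 as the sound text and 8.2 as the faulty one. 3.5 has the survival switch without the qualifier, so it needs correcting too.
- A reader might infer that events in the SAP's 28-day post-treatment window are lost. That wording, "over the treatment period (including the 28 days after the treatment discontinuation) and along the study", belongs to the deaths endpoint (just before SAP 5.4), and a dated death on a survival form satisfies it.
- A reader might take 77 to 106 as the number of patients with biased PFS. It is a ceiling that includes patients whose PFS event has already occurred.

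What the reply does not remove is the conflict itself. The other sections show that post-SU data are wanted. They do not tell a site which recording rule applies, and none gives assessment timing or says how progression is dated during second line.

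**Conclusion.** The conflict is real and should be corrected. Protocol 8.2 and 3.5 disagree on the period over which every visit is recorded. Both reduce later follow-up to six-monthly survival contact, while 8.4.1 and 8.5.3 call for fuller updates. The supportable consequence is inconsistent and possibly sparse or late capture, not loss of all post-SU events. It bears on PFS in patients who stop SU before progression, and on combined PFS, combined TTF and second-line safety.

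The divergent rules would apply to about 25 to 42 of 140 patients by month 3 and 77 to 106 by month 12. This rests on exponential stopping at the two quoted medians, which come from other populations. The count affected for first-line PFS is smaller and cannot be derived from the documents. The size of any PFS shift also depends on how far charts supply progression dates, and on censoring rules that may sit in the part of the SAP missing from the public text. The delays of 1.5 and 3.0 months are therefore illustrative.

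**What to change.** Reconcile Protocol 8.2, 3.5, 8.4.1 and 8.5.3 to one recording scope:

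- In 8.2 and 3.5, record every routine visit during SU, second-line treatment or supportive care. Include adverse events, disease status with the date of any progression found in the chart, and treatment status.
- In 8.4.1 and 8.5.3, state that the listed items apply at their scheduled months whether or not SU is ongoing.
- In 8.2 and 3.5, use the survival-only form only after second-line treatment and disease follow-up have ended. The unqualified survival bullet in 3.5 needs this correction as much as 8.2 does.
- Refer to SAP 8.2 as the analysis that needs the second-line safety data, so that collection and analysis match.

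These changes concern what is recorded. They do not change when patients are seen, scanned or treated. The cost is protocol wording and more eCRF entry per site after SU stops, taken from routine records, with no added visits or procedures.
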